#### **4.5.3 Meals and Dietary Restriction**

Participants must avoid consumption of grapefruit, pomegranates, star fruits, Seville oranges or products containing the juice of each during the entire study and preferably 7 days before the first dose of study drugs, due to potential CYP3A4 interaction with encorafenib. Orange juice is allowed.

#### **4.5.4 Activity**

Strenuous physical activities, such as competitive sports, can result in significant increases in CK levels while on binimetinib treatment. Participants should be cautioned not to start a new strenuous exercise regimen after first dose of study treatment.

### **5.0 DOSING DELAYS/DOSE MODIFICATION FOR TOXICITY**

Clinically significant adverse events or abnormal laboratory values assessed as unrelated to disease progression, intercurrent illness, or concomitant medications may require dose delay and/or dose modification. Such toxicities must have an attribution of possible, probable, or definite to encorafenib and/or binimetinib (see Section [9.3](#)). If multiple toxicities occur, dose modification decisions should be based on the most severe toxicity. If there is any question or clarification required concerning a toxicity, the treating site should contact the ABTC Central Office to determine patient's toxicity status. The ABTC Central Office, with the Study Chair (who may consult with Pfizer) will make the final decision.

#### **5.1 Dose Modification for Encorafenib and Binimetinib**

The dose levels and the general approach to encorafenib and/or binimetinib dose modification on this trial are shown below. Adverse events (AEs) should be treated with the appropriate maximum supportive care, and dose reductions should be clearly recorded on the case report form.

Dose modifications are required for any clinically significant toxicity and are defined below.

- **In general, if toxicity occurs that is attributed to only one of the agents, only that agent should be dose-reduced/modified.**
- **If administration of binimetinib is interrupted, administration of encorafenib may be continued, but at a maximal dose of 300 mg per day.**

- If administration of encorafenib is interrupted, administration of binimetinib may be continued at the same dose
- If either binimetinib or encorafenib are permanently discontinued, the other drug should also be discontinued and the patient removed from the study.

If there is any question, [name] ([contact]) or [name] ([contact]) at the ABTC Central Office and the Study Chair should be contacted.

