#### **4.4.2 Prohibited Concomitant Medications During Study**

Patients may receive other medications that the investigator deems to be medically necessary, with the specific exception of non-protocol specified chemotherapy, radiotherapy, anti-neoplastic biological therapy or other investigational agents. Patients who require the use of any of the aforementioned treatments for clinical management should be removed from the study.

Per FDA labeling, administration of encorafenib along with a strong or moderate CYP3A4 inhibitor increases encorafenib plasma concentrations and may increase adverse reactions. The use of strong inhibitors of CYP3A4 is prohibited. Concomitant administration of encorafenib with a strong or moderate CYP3A4 inducer may decrease encorafenib plasma concentrations and decrease encorafenib efficacy. Use of moderate and strong inducers of CYP3A4 is prohibited. Similarly, concomitant administration of encorafenib with sensitive CYP3A4 substrates may result in increased toxicity or decreased efficacy. Specifically, co-administration of encorafenib with hormonal contraceptives (CYP3A4 substrates) can result in decreased concentrations and loss of hormonal contraceptive efficacy. Avoid

hormonal contraceptives.

The Principal Investigator should be alerted if the patient is taking any agent known to affect or with the potential for drug interactions. The study team should check a frequently-updated medical reference for a list of drugs to avoid or minimize use thereof.

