### Recommended Binimetinib Dose Modifications \*

\*For adverse events that may be related to both encorafenib and binimetinib, guidance is provided for the other agent also.

For patients with pre-existing disorder resulting in AE >1, the new event must resolve to at least the pre-existing baseline to resume treatment following the prescribed rules as outlined in the Modification Table.

Severity of Adverse Event	Dose Modifications
Cardiomyopathy	
Asymptomatic, absolute decrease in LVEF of > 10% from baseline that is also below the LLN	Withhold binimetinib for up to 4 weeks, evaluate LVEF every 2 weeks. Resume binimetinib at one reduced dose level if the following are present: 
 
LVEF is at or above the LLN and
 
Absolute decrease from baseline is 10% or less and
 
Patient is asymptomatic.
 
 If LVEF does not recover within 4 weeks permanently discontinue binimetinib.
Grade 3-4 (Symptomatic congestive heart failure or absolute decrease in LVEF of > 20% from baseline that is also below LLN)	Permanently discontinue binimetinib. Closely monitor LVEF until resolution or up to 16 weeks.
Venous Thromboembolism	
Uncomplicated DVT or PE	Withhold binimetinib. 
 
If improves to Grade 0-1, resume at one reduced dose level.
 
If no improvement, permanently discontinue binimetinib.
 

Life threatening PE	Permanently discontinue binimetinib.
Serous Retinopathy	
Symptomatic serous retinopathy/ Retinal pigment epithelial detachments	Withhold binimetinib for up to 10 days. 
 
If improves and becomes asymptomatic, resume at the same dose.
 
If not improved, resume at one reduced dose level or permanently discontinue binimetinib.
 

Retinal Vein Occlusion (RVO)	

Severity of Adverse Event	Dose Modifications
Any Grade	Permanently discontinue binimetinib.
Uveitis	
Grade 1-3	If Grade 1 or 2 does not respond to specific ocular therapy, or for Grade 3 uveitis, withhold binimetinib and encorafenib for up to 6 weeks. 
 
• If improved, resume at same or one reduced dose level.
 
• If not improved, permanently discontinue binimetinib and encorafenib.
 

Grade 4	Permanently discontinue binimetinib and encorafenib.
Other Eye Disorders (i.e., Non-retinal Events, non-Uveitis Events)	

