- 18 – A full ophthalmic examination will be performed by an ophthalmologist at Screening, and include best corrected visual acuity, slit lamp examination, intraocular pressure, dilated funduscopy and Ocular Coherence Tomography (OCT). Examination of the retina is required, especially to identify findings associated with serous retinopathy and RVO. On study, patients receiving binimetinib should be assessed at every physical examination for decreased visual acuity using a gross perimetry test (as opposed to automated visual field testing) in person or

by telemedicine evaluation. Symptomatic patients should be referred for a full ophthalmic consultation.

\* For patients with clinical suspicion of retinal abnormalities of any grade (e.g., serous retinopathy, RVO, photopsia, metamorphopsia, impairment of visual acuity), these additional assessments should be mandatory:

- Non-vascular abnormalities: spectral domain OCT recommended
- Vascular abnormalities: fluorescein angiography of the central 30 degrees.

- 19 – Dermatology evaluation should be performed by a study team member at baseline and every 8 weeks on trial, and for up to 6 months following discontinuation of encorafenib treatment.
- 20 – Flash-frozen tissue and 20 unstained FFPE slides following guidelines in Section [9.6.5](#) should be obtained from all patients who progress and have a clinically-indicated surgical resection at time of progression.
- 21 – Surgical Arm: patients should be seen on the day of surgery (prior to surgery) to evaluate for AEs.
- 22 – Surgical Arm (and Medical Arm patients undergoing a clinically-indicated surgery for their brain tumor while on study): See “Blood” in the Table of Additional Required Observations below ([Table 9.2.1](#)) for details and also Section [9.6.5](#).
- 23 – Surgical Arm (and Medical Arm patients undergoing a clinically-indicated surgery for their brain tumor while on study): See “Tumor Tissue” in the Table of Additional Required Observations below ([Table 9.2.1](#)) for details and also Section [9.6.5](#).
- 24 – Within 3 days post-surgery.
- 25 – Surgical Arm: Pre-Cycle 1 MRI does not need to be repeated if post-surgical MRI is within 21 days of Cycle 1 start.
- 26 – The ECG replicates should be extracted from the recordings at the predefined time points (5 minutes apart (+ 5min))

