## **10.2 Off Study Criteria**

Patients will only be off study at the time of death. All patients will be followed for survival every 2 months for the first two years from the off-treatment date; after 2 years, patients will be followed every 6 months until death. Survival status may be obtained by phone call, clinic visit, or medical records (e.g. physician notes/laboratory results of clinic or hospital visit). Please note that additional survival status reports will be required twice yearly for ABTC Central Office reporting.

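### Sections 5.1 and 4.4.2 remove patients from the study while Section 10.2 keeps everyone on study until death, so a site could end follow-up early

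*Combined protocol and SAP*

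**What the plan says.** Section 5.1 (Dose Modification) sets the rule for a permanent stop of either drug: "the other drug should also be discontinued and the patient removed from the study". Section 4.4.2 (Prohibited Concomitant Medications) says that patients who need non-protocol anticancer treatment or another investigational agent "should be removed from the study".

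Section 10.2 (Off Study Criteria) says: "Patients will only be off study at the time of death". It continues: "All patients will be followed for survival every 2 months for the first two years from the off-treatment date", with contact every 6 months after that until death.

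Section 10.1 lists an unacceptable adverse event as a reason for going off treatment. It also asks the case report form to record the reason and date of study removal, separately from those of stopping therapy.

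Several places require safety follow-up after drug is stopped:
- Sections 9.3 and 10.0 and Table 9.1 footnote 9: adverse events for at least 30 days after the last dose.
- Section 9.4.2: serious adverse events that are related, or of unknown relationship, until they resolve or are judged chronic or stable.
- Binimetinib dose table, Grade 3-4 cardiomyopathy: "Closely monitor LVEF until resolution or up to 16 weeks".
- Both dose tables, other eye disorders that lead to a permanent stop: ophthalmic monitoring until stable or resolved.
- Table 9.1 footnote 19: dermatology evaluation "for up to 6 months following discontinuation of encorafenib treatment".

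**The concern.** A site turns to Section 5.1 when a serious toxicity occurs, and to 4.4.2 when a patient needs another therapy. Both send the patient out of the study. A site that does this literally, and enters a study-removal date on the form, has grounds to stop survival contact and later safety checks.

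Overall survival is secondary objective 4. If contact ended at drug stop, the patients lost would be selected by toxicity or by need for other treatment. Both can be related to prognosis, so the censoring could be informative, which the Kaplan-Meier method in Section 11.3 assumes it is not. The safety items most exposed are those that run well past 30 days, because a site that regards the patient as gone has least reason to schedule them.

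**Working it through.** **1. The plan's own figures, as background.** Section 11.2 gives a two-stage design for each primary cohort: 14 patients, stop if 1 or fewer respond; otherwise 23 patients, success if 5 or more respond; null rate 10%, alternative 30%.
- Early stopping at 10%: 0.9^14 + 14 × 0.1 × 0.9^13 = 0.2288 + 0.3559 = 0.585 (stated: at least 0.58).
- Probability of success: the sum over x = 2 to 14 of P(X1 = x) × P(X2 ≥ 5 − x), with X1 binomial on 14 and X2 binomial on 9. This gives 0.070 at 10% (stated ceiling 10%) and 0.853 at 30% (stated: at least 85%).

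The figures reproduce. Follow-up status after drug stop does not enter them, so the primary analysis is not touched.

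**2. The passages side by side.**

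| Event | 5.1 or 4.4.2 | Section 10 |
|---|---|---|
| Permanent stop of one drug for toxicity | Other drug stopped; patient removed from study | Off treatment (10.1); on study until death (10.2) |
| Need for other anticancer therapy | Patient removed from study | Not listed by name in 10.1; on study until death (10.2) |
| Survival contact after the stop | None implied | All patients, from the off-treatment date |

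The protocol treats the two states as different: 10.1 and 10.2 are separate sections, and Section 5.3 speaks of removal from treatment, not from the study. So the phrase in 5.1 and 4.4.2 cannot simply be taken as another name for off treatment. Section 10.1 also makes study removal a dated entry on the form.

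**3. How overall survival would handle a removed patient.** Section 11.3 censors a patient who is alive at data cut-off. It gives no rule for a patient whose contact ended earlier. Under 10.2 this should seldom arise; under a literal 5.1 it would arise for every toxicity stop.

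**4. Scale.** The documents give no rate of permanent discontinuation. With an assumed rate d, the number exposed is d × n.
- Primary cohort, n = 23: 0.05 × 23 = 1.15 and 0.20 × 23 = 4.6, about 1 to 5 patients.
- Maximum enrolment, n = 62: 0.05 × 62 = 3.1 and 0.20 × 62 = 12.4, about 3 to 12 patients.

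These are ceilings for the chosen rate, because they count every such patient as lost. They do not count patients under 4.4.2, for whom the documents give no basis for a figure.

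**The case against.** The strongest reply is that Section 10 governs disposition and is clear. It classes a toxicity stop as off treatment, follows all patients for survival without exception, accepts a phone call or medical records as the source, and requires extra survival reports to the Central Office twice a year, which would reveal a site that had stopped contact. Section 5.1 sends questions to the Central Office and the Study Chair. The tables under 5.1 order monitoring after a permanent stop, so the natural reading of the phrase is removal from study treatment.

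Most of this stands. It defeats two stronger readings that a reader might infer. One is that the plan leaves toxicity-stopped patients without follow-up, or censors their survival at drug stop. Sections 10.2 and 11.3 say neither; that would be a site departure from 10.2. The other is that recovery from the most serious events would go unrecorded. Section 9.4.2 follows related serious events to resolution or stability. The 16-week LVEF rule covers only Grade 3-4 cardiomyopathy, so it is not at stake for every toxicity stop.

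What the reply does not remove is the contradiction itself. A site has to guess that 10.2 overrides 5.1, and the form invites a study-removal date that 10.2 does not allow before death.

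**Conclusion.** The concern holds as a conflict of wording with a practical risk. Sections 5.1 and 4.4.2 cannot both be followed alongside 10.2, and a site that chooses the former could end survival follow-up early in a group selected by toxicity or by need for other therapy. Some longer safety follow-up could go with it: LVEF after Grade 3-4 cardiomyopathy, ophthalmic monitoring, and dermatology for up to 6 months.

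The size is modest. About 1 to 5 of 23 patients per primary cohort is an upper limit, resting on an assumed 5% to 20% discontinuation rate and on every such patient being lost. No bias in the survival estimate can be calculated from the documents. With cohorts this small and analysed separately, though, a few early losses can matter to a Kaplan-Meier curve. The primary response endpoint and its two-stage design are unaffected.

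**What to change.** Reconcile Sections 5.1 and 4.4.2, and the study-removal entry in 10.1, with Section 10.2:
- In 5.1 and 4.4.2, state that these patients are not off study, that survival follow-up continues under 10.2, and that safety follow-up continues where Sections 9.3, 9.4.2 and 10.0, Table 9.1 and the dose tables already require it.
- In 4.4.2, limit the change to follow-up status. Section 10.1 does not name the need for other anticancer therapy as an off-treatment reason, so the sponsor should reconcile those two passages as well.
- In 10.1, say which events the study-removal entry records, so that a toxicity stop is not entered there.

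Leave the rules on when each drug is stopped unchanged. The cost is a few sentences in an amendment and a note to sites on completing the form. The follow-up is already planned, so no visit or procedure is added.

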#### Dose Reduction Schedule for Encorafenib

Dose Level	Encorafenib Dose/Schedule
0	450 mg daily
-1	300 mg daily
-2	225 mg daily
-3	150 mg daily

#### Dose Reduction Schedule for Binimetinib

Dose Level	Binimetinib Dose/Schedule
0	45 mg twice daily
-1	30 mg twice daily
-2	15 mg twice daily

#### Recommended Encorafenib Dose Modifications \*

\*For adverse events that may be related to both encorafenib and binimetinib, guidance is provided for the other agent also.

For patients with pre-existing disorder resulting in AE >1, the new event must resolve to at least the pre-existing baseline to resume treatment following the prescribed rules as outlined in the Modification Table.

Severity of Adverse Event	Dose Modifications
New Primary Malignancies	
Non-cutaneous RAS mutation-positive malignancies	Permanently discontinue.
Uveitis	
Grade 1-3	If Grade 1 or 2 does not respond to specific ocular therapy, or for Grade 3 uveitis, withhold encorafenib and binimetinib for up to 6 weeks. 
 
• If improved, resume encorafenib and binimetinib at same or one reduced dose.
 
• If not improved, permanently discontinue encorafenib and binimetinib.
 

Grade 4	Permanently discontinue encorafenib and binimetinib.
Other Eye Disorders (i.e., non-Uveitis Events)	

Severity of Adverse Event	Dose Modifications
Grade 1–2	Maintain dose level of encorafenib and binimetinib and increase frequency of ophthalmic monitoring to at least every 14 days until stabilization or resolution.
Grade 3	
Interrupt dosing of encorafenib and binimetinib and refer patient to ophthalmologist within 7 days.
 
 
• If resolved to Grade <math>\leq 1</math> in <math>\leq 21</math> days, resume treatment at one reduced dose level of encorafenib and binimetinib.
 
• If not resolved to Grade <math>\leq 1</math> in <math>\leq 21</math> days, permanently discontinue encorafenib and binimetinib and close follow-up with ophthalmic monitoring until stabilization or resolution.
 

Grade 4	Permanently discontinue encorafenib and binimetinib and immediate follow-up with ophthalmic monitoring ( refer to footnote 18 of Table 9-1 ) until stabilization or resolution.
QTc Prolongation	
QTc > 500 ms and $\leq 60$ ms increase from baseline	
1st - 2nd occurrence:
 
 
• Temporarily interrupt dosing of encorafenib until QTc < 500 ms. Then resume treatment at 1 reduced dose level of encorafenib.
 
 
3rd occurrence:
 
 
• Permanently discontinue encorafenib.
 

QTc > 500 ms and > 60 ms increase from baseline	Permanently discontinue.

Severity of Adverse Event	Dose Modifications
Hepatotoxicity	
Grade 2 AST or ALT	Maintain encorafenib dose. 
 
If no improvement within 2 weeks, withhold encorafenib until improved to Grade 0-1 or to pretreatment/baseline levels and then resume at the same dose.
 

Grade 3 or 4 AST or ALT increased	See Other Adverse Reactions
Dermatologic (Except Hand-foot Skin Reactions)	
Grade 2	Initiate supportive measures: 
 
Avoid unnecessary sunlight, apply broad-spectrum sunscreen at least twice daily.
 
Use mild-strength topical steroid (hydrocortisone 1% cream) or topical antibiotic (e.g., clindamycin) OR oral antibiotics (e.g., doxycycline 100 mg BID, minocycline 100 mg BID)
 
 
If no improvement within 2 weeks, withhold encorafenib until Grade 0-1. Resume at same dose if first occurrence or reduce one dose level if recurrent.

Grade 3	Initiate supportive measures above. Withhold encorafenib until Grade 0-1. Resume at same dose if first occurrence or reduce one dose level if recurrent.
Grade 4	Permanently discontinue encorafenib.
Hand-foot Skin Reaction (HFSR)/Palmar-plantar Erythrodysesthesia Syndrome (Dose Adjustment for Encorafenib ONLY)	
Grade 1	Maintain dose of encorafenib. Promptly institute supportive measures, such as topical therapy, for symptomatic relief. Give instruction on life-style modifications.
Grade 2	1 st occurrence: 
 
Maintain dose of encorafenib and HFSR should be closely monitored. Promptly institute supportive measures, such as topical therapy, for symptomatic relief. Give instruction on life-style modifications.
 
If no improvement <math>\leq</math> 14 days, interrupt dosing of encorafenib until resolved to Grade <math>\leq</math> 1. Resume treatment with encorafenib at current dose level. Continue supportive measures, such as topical therapy, for symptomatic relief. Give instruction on life-style modifications.
 
 
Additional occurrence:

Severity of Adverse Event	Dose Modifications
Grade 3	
 
Treatment with encorafenib may be maintained or interrupted based upon the Investigator's discretion. Continue supportive measures, such as topical therapy, for symptomatic relief. Give instruction on life-style modifications.
 
 
If interrupted dosing of encorafenib per Investigator's judgment, interrupt until resolved to Grade <math>\leq</math> 1. Resume treatment with encorafenib at the same dose level or one reduced dose level based upon the Investigator's discretion.
 
1st or additional occurrence:  Interrupt dosing of encorafenib until resolved to Grade <math>\leq</math> 1. Promptly initiate supportive measures, such as topical therapy, for symptomatic relief. Give instruction on life-style modifications. Reassess the patient weekly. Then resume treatment at one reduced dose level of encorafenib.
 
 
Consider referral to dermatologist and manage HFSR per dermatologist's recommendation.
 
 
> 3rd occurrence:  Interrupt dosing of encorafenib until resolved to Grade <math>\leq</math> 1, decision to resume treatment with encorafenib at one reduced dose level or permanently discontinue encorafenib should be based upon the Investigator's discretion.

Nausea/Vomiting	
Grade 1-2	Maintain dose level of encorafenib and binimetinib. Promptly institute antiemetic measure.
Grade 3	Interrupt dosing of encorafenib and binimetinib until resolved to Grade $\leq$ 1. Then resume treatment at one reduced dose level of encorafenib. Resume treatment with binimetinib at the current dose if, in the judgment of the Investigator, the toxicity is considered to be unrelated to binimetinib, or at one reduced dose level. Note: Interrupt dosing of encorafenib and binimetinib for $\geq$ Grade 3 vomiting or Grade 3 nausea only if the vomiting or nausea cannot be controlled with optimal antiemetics (as per local practice).
Grade 4	Permanently discontinue encorafenib and binimetinib.
Other Adverse Reactions (including renal, hemorrhage).	
Recurrent Grade 2 or First occurrence of any Grade 3	Withhold encorafenib for up to 4 weeks. 
 
If improves to Grade 0-1 or to pretreatment/baseline levels, resume at one reduced dose level.
 
If no improvement, permanently discontinue.
 

First occurrence of any Grade 4	Permanently discontinue encorafenib or withhold for up to 4 weeks.

Severity of Adverse Event	Dose Modifications
	
 
If improves to Grade 0-1 or to pretreatment/baseline levels, then resume at one reduced dose level.
 
If no improvement, permanently discontinue.
 

Recurrent Grade 3	Consider permanently discontinuing.
Recurrent Grade 4	Permanently discontinue.

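### For eye events that may relate to both drugs, the two Section 5.1 tables give conflicting binimetinib instructions for Grade 1–3 RVO and for symptomatic serous retinopathy, and no written rule says which governs

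*Combined protocol and SAP*

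**What the plan says.** Section 5.1 has one dose-modification table per drug. Both carry the same note: "For adverse events that may be related to both encorafenib and binimetinib, guidance is provided for the other agent also".

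The encorafenib table has a uveitis block and then a block headed "Other Eye Disorders (i.e., non-Uveitis Events". Its instructions name both drugs:
- For Grade 1–2, the rule is: "Maintain dose level of encorafenib and binimetinib and increase frequency of ophthalmic monitoring to at least every 14 days until stabilization or resolution".
- For Grade 3, the rule is: "Interrupt dosing of encorafenib and binimetinib and refer patient to ophthalmologist within 7 days". If the event falls to Grade 1 or less within 21 days, both drugs restart one level lower; otherwise both stop for good.
- For Grade 4, the rule is: "Permanently discontinue encorafenib and binimetinib and immediate follow-up with ophthalmic monitoring".

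The binimetinib table has nearly the same block under a narrower heading, "Other Eye Disorders (i.e., Non-retinal Events, non-Uveitis Events". Retinal events have their own rows there. RVO of any grade means permanent discontinuation of binimetinib. Symptomatic serous retinopathy or RPE detachment, with no grade given, means "Withhold binimetinib for up to 10 days". What follows depends on the outcome: "If improves and becomes asymptomatic, resume at the same dose". Without improvement, binimetinib restarts one level lower or is stopped.

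Three general rules in Section 5.1 bear on this. A toxicity attributed to one drug changes only that drug. While binimetinib is interrupted, encorafenib may go on at no more than 300 mg daily. Permanent discontinuation of either drug ends the other and removes the patient from the study.

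**The concern.** The two eye blocks look like a matched pair, but only one excludes retinal events. Read literally, the encorafenib table gives binimetinib instructions for RVO and serous retinopathy that differ from those in the table written for binimetinib.

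This is a patient-safety rule. Section 5.1 calls dose modifications required for clinically significant toxicity, although the table titles say recommended. A site that follows the encorafenib block exactly would keep binimetinib going after Grade 1–2 RVO and could restart it after Grade 3 RVO. A site that follows the binimetinib table would end both drugs. Patients with the same event could be managed differently at different sites, each in line with the protocol.

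**Working it through.** No sample size, power or event figure is involved. The check sets the two tables side by side, looks for a ranking rule, and then works out the dose difference.

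**1. Instructions for binimetinib, event possibly related to both drugs**

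| Event | Encorafenib table | Binimetinib table | Result |
|---|---|---|---|
| RVO, Grade 1–2 | continue unchanged | permanent stop | conflict |
| RVO, Grade 3 | interrupt; one level lower if resolved within 21 days, else stop | permanent stop | conflict |
| RVO, Grade 4 | permanent stop | permanent stop | agree |
| Symptomatic serous/RPE, Grade 1–2 | continue unchanged | hold up to 10 days; same dose if improved and symptom-free, else one level lower or stop | conflict |
| Symptomatic serous/RPE, Grade 3 | interrupt; one level lower if resolved within 21 days, else stop | as above | conflict on hold length and, if improved, on restart dose |
| Symptomatic serous/RPE, Grade 4 | permanent stop | as above | conflict, unless the event has not improved and the site chooses to stop |

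**2. Is there a ranking rule?**
- Section 5.0, most severe toxicity: chooses between several toxicities, not between two tables for one toxicity.
- Sections 5.0 and 5.1, Central Office and Study Chair: decide when a question is raised.
- Section 5.1, one-drug attribution: settles the case where only binimetinib is blamed, and is silent when both may be.
- Section 5.2: bars re-escalation of either drug after a reduction for retinal toxicity of Grade 2 or more, but does not rank the tables.

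None says which table prevails.

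**3. Dose difference per patient**, assuming full dose at onset (encorafenib 450 mg daily, binimetinib 45 mg twice daily; dose-level tables, Section 5.1)
- RVO, Grade 1–2: 450 mg encorafenib plus 2 × 45 = 90 mg binimetinib daily, against neither drug.
- Serous/RPE, Grade 1–2: no change, against a binimetinib hold of at most 10 × 2 = 20 doses, or 20 × 45 = 900 mg, with encorafenib capped at 300 mg, which is (450 − 300)/450 = 33.3% lower. The 900 mg is a maximum. For a patient already at 300 mg or less, the cap changes nothing.
- Serous/RPE, Grade 3, resolved: binimetinib restarts at 30 mg twice daily, (45 − 30)/45 = 33.3% lower, and Section 5.2 bars re-escalation. The other table restarts it at 45 mg twice daily if the patient is improved and symptom-free. The recovery windows differ by 21 − 10 = 11 days.

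**The case against.** The strongest reply is that this is a drafting slip with an obvious answer. The blocks are nearly identical, one heading lacks a phrase, and a site deciding on binimetinib after RVO would naturally turn to the named row in the binimetinib table. Once that row is read, the linked-discontinuation rule stops both drugs. Suspected retinal abnormality of any grade also triggers extra eye assessments (Section 4.1), and open questions go to the Central Office. All of this lowers the risk. But that the specific row prevails is an inference, and the Central Office route does not help a site that reads one table and sees no question. Letting each table govern only its own drug contradicts the note on both tables. It also fails at Grade 4 serous retinopathy: the encorafenib table stops encorafenib, the linked rule then stops binimetinib, yet the binimetinib row may allow a restart.

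The supporting evidence that the encorafenib block was meant to cover retinal events is modest. Its Grade 4 row cites footnote 18 of the Section 9.1 observation table, which mentions serous retinopathy and RVO but describes a full eye examination. Section 5.2 foresees encorafenib reductions for retinal toxicity, but those could come from the rows for other adverse reactions. The point rests on the heading as written.

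Three stronger readings should be resisted.
- A reader might infer that the conflict is common, because Table 9-5 lists RPE detachment as very common and chorioretinopathy as common. That is a list for the combination, without category definitions, symptomatic share, grade or attribution. Among eye disorders, the single-agent encorafenib list (Table 9-3) names only iridocyclitis, while retinopathy and retinal vascular occlusion (the latter under 3%) are on the binimetinib list (Table 9-4), so many events may be attributed to binimetinib alone.
- A reader might infer that the binimetinib row always ends in a same-dose restart. It does so only if the patient improves and becomes symptom-free.
- A reader might infer that a new grade-by-grade regimen is needed. The documents show two existing rules in conflict, not that both are wrong.

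**Conclusion.** The contradiction is real and worth correcting. For events that may relate to both drugs, the tables conflict for RVO at Grades 1–3 and for symptomatic serous retinopathy or RPE detachment at every grade, apart from branches that happen to reach the same outcome. RVO is the clearest case: unchanged dosing against the end of both drugs and removal from the study.

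This assumes that the encorafenib block heading means what it says and that the investigator does not attribute the event to binimetinib alone. The dose figures also assume full dose at onset. No patient count can be given. The named binimetinib rows and the Central Office route reduce the risk without removing it.

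**What to change.** 1. Exclude RVO from the encorafenib table's other-eye block and add a row to that table: RVO, any grade, permanently discontinue both drugs. The binimetinib row and the linked-discontinuation rule already imply this.
2. Add one sentence to Section 5.1: for symptomatic serous retinopathy or RPE detachment of Grade 1–2, the binimetinib row governs binimetinib, with encorafenib at most 300 mg daily while binimetinib is held.
3. For Grade 3–4 symptomatic serous retinopathy or RPE detachment, the study team should choose one of the two existing rules and word it identically in both tables. Until then, keep the encorafenib table's Grade 4 stop of both drugs. No new regimen is proposed here.

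Simply adding non-retinal to the encorafenib heading would be shorter, but it would remove that Grade 4 stop. It would also leave other retinal events, such as chorioretinitis and retinal detachment (Table 9-4, footnote 3), without an eye row in either table, although the rows for other adverse reactions would still catch the more serious ones.

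The cost is one row, one exclusion, one sentence and a clinical decision on Grade 3–4, in the next amendment with a note to sites. Sample size, visits and analysis do not change.
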